National Co-Principal Investigator Heart Failure Cardiologist	[name] Chief, Division of Cardiovascular Medicine Ohio State University [contact]
Manufacturer	Sunshine Heart, Inc. [name] Tele: [name] [contact] www.sunshineheart.com

Clinical/Technical Support [contact]-SHPULSE)

INTRODUCTION

PURPOSE

Sunshine Heart Inc. is sponsoring a prospective, multi-center trial to assess the safety and provide indications for performance of the Sunshine Heart C-Pulse® System (“C-Pulse®”).

The purpose of the study is to determine whether use of C-Pulse® as treatment for patients in moderate to severe heart failure (HF) is associated with reasonable assurance of safety and performance, such that the C-Pulse® merits Food and Drug Administration (FDA) approval for continuation into a pivotal study to examine the safety and efficacy of C-Pulse® for US market approval.

STUDY SIZE AND DURATION

This clinical study is expected to commence September 2008. The duration of the study is expected to be 120 months. The primary study population will include 20 patients enrolled and implanted with C-Pulse® in up to 7 centers in the United States (US) and potentially some Outside the United States (OUS) centers. This expansion protocol will allow 40 patients to be enrolled and implanted in up to 9 centers. The first 40 patients that meet all eligibility criteria will proceed to implantation. Up to approximately 60 patients will be enrolled and consented for performing screening and testing required to confirm eligibility, such as Computed Tomography (CT) scan. All patients must be consented prior to performing any study related procedures. A patient is considered enrolled upon signing the informed consent. To minimize the burden to the patient, data collected as standard of care and not for the specific reason for study eligibility may be used for baseline data points as outlined in the informed consent. These tests will suffice for the baseline dataset if collected within the screening timeframe of 30 days prior to implant.

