The study is designed to assess the safety and potential benefit of the C-Pulse® System before initiating a wider randomized clinical trial to demonstrate safety and effectiveness. The effect of the C-Pulse® system in relieving heart failure symptoms in patients with ACC/AHA Stage C, NYHA Class III-ambulatory Class IV heart failure will be documented with this study.

This Feasibility Study is multi-center study which is being expanded to include up to 9 centers in the US and potentially some OUS centers. The study population will be expanded to include 40 patients enrolled and implanted with the C-Pulse® System. The period of follow-up for the initial 20 patients will be 6 months to assess the safety and performance before initiating the pivotal clinical trial. It is desired that the system be used all the time. However, the System should not be “Off” for greater than one hour at any one time for a maximum of four hours total per day during the study period. For the extent of the trial period (6 months), C-Pulse® should be used at least 20 hours per day (i.e. device must be used greater than 80% of the time). The patient must limit the duration of disconnection to 15 minute intervals for a maximum of 4 hours total during the trial period to ensure the device is used for 80% of the time. The Driver logs patient usage automatically and stores into the system files.

Patients will be followed for up to 10 years or until the study is closed.

If a patient undergoes anesthesia for the purpose of C-Pulse implantation but does not receive a C-Pulse System, the patient will be followed until 30 days or discharge whichever occurs first.

[figure not shown]

Figure 1A. Study Design

Patients will be enrolled into the trial upon providing informed consent. Procedures related directly to the study must not be performed prior to informed consent. Data collection will be noted prior to implantation of the device and at one, three, and six months following implant and then long term at 12 and 18 months followed by annually post-implant for five years. Adverse events will be collected throughout the study until study closure and will be adjudicated by the Clinical Event Committee (CEC).

Progress reports of the clinical outcomes will be reviewed by the DSMB after enrollment of five (5) patients and twice per year thereafter, unless slow enrollment does not warrant this meeting frequency.

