- Inadequate device tracking or off-label investigator device use
- Failure to follow-up patients per scheduled follow-ups
- Failure to submit data in a timely manner
- Failure to follow-up with findings on a monitoring report

Note that any patients previously enrolled will continue to be followed at this institution by the investigator or a named co-investigator.

Laboratory Accreditation and Normal Values

Before initiation of the study, appropriate accreditation for all laboratories to be used in the study must be provided to the sponsor. Throughout the study, the Investigator must provide documentation of all renewals of accreditation. The ranges of values considered normal for the laboratory tests being performed for the study must be provided to Sponsor in order to facilitate pooling of the data.

PROCEDURES

Screening and Patient Informed Consent

Prior to enrolling patients, each investigational center IRB will be required to approve the study Investigation Plan, and the Patient Informed Consent. In addition, patients will be required to provide written informed consent for enrollment. A Screening Log is located within the site Regulatory Binder and should be completed for all patients screened but not enrolled for the study.

Patients will undergo a pre-implant baseline assessment to ensure they meet the inclusion and exclusion criteria no more than **30 Days** prior to the implant date. Patient informed consent must be signed prior to conducting any screening or baseline testing procedure performed for study purposes. **When a patient signs an informed consent for the study, he/she is considered enrolled in the study and will be assigned a study identification number by the center.** To minimize the burden to the patient, data collected as standard of care and not for the specific reason for assessing study eligibility may be used for baseline data points as outlined in the informed consent. These tests will suffice for the respective portion of the baseline dataset if collected within the pre-implant evaluation timeframe of 30 days prior to implant. Upon completion of screening, all patients that do not satisfy the eligibility criteria will be promptly study exited without proceeding to implantation. Study Exit of these patients must be documented on the Study Exit Form. Any patient whom undergoes anesthesia for the purpose of C-Pulse implantation but does not receive the device will be monitored for adverse events as

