Assessment will be made of the intima for the degree of atherosclerotic ascending aortic disease, specifically: Nil, Mild (intimal thickening less than or equal to 3 mm), Moderate (intimal thickening greater than 3mm or mobile atheroma) or Severe (mural calcification)¹⁷. The CT Scan Core Lab will assess the outcome of the test for acceptability. Data will be completed on the Baseline and Follow-up eCRFs.

NOTE: Contrast-induced nephropathy must be evaluated within one week post-baseline CT scan. Patients with an increase in Creatinine ≥ 0.5 mg/dL or a greater than 20% reduction in GFR must be followed until resolution of the decrease in renal function. This will be tracked as an observation via the follow-up form and should not be reported as an adverse event.

Neurological Assessment - (pre-implant, pre-discharge, 1, 3 and 6 month follow-ups)

A series of tests/assessments are required to assess for the presence of neurological dysfunction. Outlined below is the required assessment tool and specific required interval for collection:

NIH Stroke Scale and Modified Rankin

NIH Stroke Scale (NIHSS) is the standardized assessment tool for screening for any unobserved neurological dysfunction. The Modified Rankin is a standardized assessment tool for scoring disability status and/or ability to function. The NIHSS and Modified Rankin are required at pre-implant, at pre-discharge, 1, 3 and 6 months post implant. In the case of a neurological dysfunction adverse event, the NIHSS and Modified Rankin are required at 30 and 60 days post event in addition to the regular follow-up schedule. Clinicians performing the NIHSS and Modified Rankin are required to be trained. Clinicians performing NIHSS must also be certified prior to performing the assessment. Access to required training and certification tools will be provided in the study activation training for the study personnel designated for collecting the NIHSS. A neurological consultation is also required if an increase of 2 or more is noted on the NIHSS.

Head CT Scan

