Any new, temporary or permanent, focal or global neurological deficit ascertained by a standard neurological examination (administered by a neurologist or other qualified physician and documented with appropriate diagnostic tests and consultation note). The examining physician will distinguish between a transient ischemic attack (TIA), which is fully reversible within 24 hours (and without evidence of infarction), and a stroke, which lasts longer than 24 hours (or less than 24 hours if there is evidence of infarction). The NIH Stroke Scale and Modified Rankin (for patients > 5 years old) must be re-administered at 30, 60 and 90 days following the event to document the presence and severity of neurological deficits. Each neurological event must be subcategorized as:

- 1) Transient Ischemic Attack (acute event that resolves completely within 24 hours with no evidence of infarction)
- 2) Ischemic or Hemorrhagic Cardiovascular Accident/CVA (event that persists beyond 24 hours or less than 24 hours associated with infarction on an imaging study)

Psychiatric Episode

Disturbance in thinking, emotion or behavior that causes substantial impairment in functioning or marked subjective distress requiring intervention. Intervention is the addition of new psychiatric medication, hospitalization, or referral to a mental health professional for treatment. Suicide is included in this definition.

Renal Dysfunction

Two categories of renal dysfunction will be identified:

Acute Renal Dysfunction

Abnormal kidney function requiring dialysis (including hemofiltration) in patients who did not require this procedure prior to implant, or a rise in serum creatinine of

greater than 3 times baseline or greater than 5 mg/dL (**in children**, creatinine greater than 3 times upper limit of normal for age) sustained for over 48 hours.

Chronic Renal Dysfunction

An increase in serum creatinine of 2 mg/dl or greater above baseline, or requirement for hemodialysis sustained for at least 90 days.

NOTE: Contrast-induced nephropathy must be evaluated within one week post-baseline CT scan. Patients with an increase in Creatinine ≥ 0.5 mg/dL or a greater than 20% reduction in GFR must be followed until resolution of the decrease in renal function. This will be tracked as an observation via the follow-up form and should not be reported as an adverse event.

Respiratory Failure

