Safety will be represented in the composite device-related adverse event rate which will be reported with its 95% two-sided exact confidence interval. The composite device-related adverse event rate will be assumed to follow the Binomial Distribution. The DSMB will decide the clinical acceptability of this observed event rate in assessing trial success.

Additionally each event will be presented with its respective rate and confidence interval. Death will be separated into deaths that occur before 30-days post-procedure and those that occur between 30-days post-procedure and 6 months.

Efficacy measurements

The efficacy of C-Pulse® will be evaluated by assessing the change of the efficacy variables from baseline to 6 months post-implant. The following measurements will be taken at baseline and 6-months.

- Peak VO₂
- Quality of Life as measured by the Minnesota Living with Heart Failure (MLWHF)
- HF Symptoms as measured by NYHA
- Six Minute Hall Walk Test

Performance Requirement

Trial success will be evaluated by analyzing each patient's response to the four efficacy variables. A responder analysis will be performed for each patient assessing the response to each of the four efficacy variables. Each efficacy variable will be assessed for clinical improvement ("responder"), decline ("non-responder") or no change ("indeterminant").

Clinical improvement will be defined for each efficacy variable as:

- 1.2 ml/kg/min improvement in peak VO₂
- 7 point improvement in MLWHF score
- 1 class improvement in NYHA
- 50 meter improvement in the Six Minute Hall Walk

Clinical decline will be defined for each efficacy variable as:

- 1.2 ml/kg/min decrease in peak VO₂
- 7 point decrease in MLWHF score
- 1 class decrease in NYHA
- 50 meter decrease in the Six Minute Hall Walk

A patient that shows no improvement or decline in a particular endpoint will be labeled as "indeterminate" for that endpoint.

The overall percentage of responders, non-responders and indeterminates for each efficacy variable along with the respective 95% two-sided exact confidence interval will be presented. Additionally the point estimate for the average change and its respective standard deviation will be presented for peak VO₂, MLWHF, and the Six Minute Hall Walk. The improvement in NYHA will be presented by a cross-tabulation summary. The DSMB will decide the clinical acceptability of this responder analysis in assessing trial success.

Secondary Objectives

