The presence of a percutaneous line creates a risk of long-term infection at the exit-site and specific guidelines are given to care-givers and patients for managing this wound site long-term. The percutaneous lead has been specifically designed to reduce the risk of infection – the outside diameter is approximately 5 mm, the material is Silicone, and the tubing is soft and flexible. Flockings exist subcutaneously to anchor the Lead in a manner similar to Tenckhoff and Hickman catheters.³⁴ There is no device ‘pocket’ created.

The Cuff and ECG lead can be terminated subcutaneously and sealed if the Percutaneous Lead is chronically infected or otherwise damaged and needs removal.

Risks Related to the Study Conduct

The methods for data collection involve only standard, well-established methods and do not differ from normal mechanical circulatory support device implantation and heart failure management follow-up practice. Therefore, the clinical study requirements of C-Pulse® pose no additional risk to the patient.

Risk Minimization

Sunshine Heart has attempted to minimize the risk of implanting the C-Pulse® through careful design and pre-clinical testing. Preclinical testing includes bench and animal testing to verify performance, software validation testing, destructive analysis and shock tests, and packaging qualifications.

Risks normally associated with cardiac devices and their implantation will be minimized by selecting investigators who are experienced in the diagnosis and treatment of patients with end-stage heart failure. In addition, investigators will be trained on the device operation and protocol prior to participating in the study. Product labeling is also provided which further addresses risk mitigation.

³⁴[Ash 1990]

Prior to implant patients should go through a complete cardiac evaluation. After implantation, patients will be followed at regular intervals to confirm that the device parameters are appropriate and to monitor the status of the C-Pulse® system. Frequent follow-up will promote faster identification and resolution of adverse events. The severity of system related events will be minimized by restricting use of the C-Pulse® to hospitals equipped with redundant systems and staffed by qualified, trained personnel.

C-Pulse® Potential Benefits

Anticipated benefits of the C-Pulse® may include:

- Relief of symptoms
- Improved QOL
- Enhanced mobility
- Home discharge

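### Harm collection has three gaps: it ends early after an aborted implant, exempts contrast kidney injury without a severity limit, and does not tie screen-failure exit to the renal check

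*Combined protocol and SAP*

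**What the plan says.** **Aborted implants.** For a patient anesthetized for implantation who receives no device, Study Description, Design states: "the patient will be followed until 30 days or discharge whichever occurs first". Screening and Patient Informed Consent applies the same limit to adverse-event monitoring.

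**Contrast kidney injury.** The CT Scan paragraph of Summary of Required Testing asks for contrast at baseline. Its note, repeated inside the Renal Dysfunction definition, says: "Contrast-induced nephropathy must be evaluated within one week post-baseline CT scan". A creatinine rise of at least 0.5 mg/dL or a GFR fall above 20% must be followed to resolution. The note ends: "This will be tracked as an observation via the follow-up form and should not be reported as an adverse event". It names no severity ceiling. The same definition counts dialysis, or creatinine above 3 times baseline or above 5 mg/dL sustained beyond 48 hours, as acute renal dysfunction. A rise of 2 mg/dL or more, or hemodialysis sustained for at least 90 days, counts as chronic.

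**Screen failures.** Screening and Patient Informed Consent says: "all patients that do not satisfy the eligibility criteria will be promptly study exited without proceeding to implantation". Study Size and Duration and Pre-implant Preparation say the same in substance. The planning counts are in Study Size and Duration: "Up to approximately 60 patients will be enrolled and consented for performing screening and testing required to confirm eligibility", and "The first 40 patients that meet all eligibility criteria will proceed to implantation".

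**What the analysis expects.** The first primary objective is framed by serious adverse event rates. The statistical section tabulates events by seriousness, device-relatedness and procedure-relatedness. Performance Requirements says: "Death will be separated into deaths that occur before 30-days post-procedure", with a second interval running to 6 months. Subjects for Analysis restricts the primary set to patients with the device placed and opens the secondary set to all followed-up subjects.

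**The concern.** The study is meant to describe risk before a pivotal trial, and the collection rules are narrower than the reporting plan they feed.

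An aborted implant is foreseeable. Epi-aortic ultrasound is performed at implant to confirm the absence of significant aortic disease, and the aortic circumference is measured after the chest incision. The Risk Analysis describes the procedure as a median sternotomy and lists bleeding, infection, neurological dysfunction, wound dehiscence and death among its risks. Under the earlier-of rule, the 30-day limit acts only on a patient still in hospital at day 30; for everyone else, collection stops at discharge.

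The contrast note applies to every contrast-exposed patient, implanted or not. The Clinical Events Committee reviews adverse events, and no route is stated by which an observation reaches it. The protocol's other exemption list, Unavoidable Events, is confined to minor events, most with a time limit; the contrast note has neither restriction.

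For screen failures, an instruction to exit promptly and an instruction to check and follow renal function stand in different sections without reference to each other.

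The Risks Related to the Study Conduct section says that study requirements "pose no additional risk to the patient". That statement can be tested only if such events are collected and classified.

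**Working it through.** **1. Planning counts (Study Size and Duration).** Consented, at most about 60; implanted, 40. Not implanted: 60 − 40 = 20, and 20/60 = 33%. The older figures in Sample Size Determination (20 implanted, up to about 10 more enrolled) give the same share: 10/30 = 33%. This is a ceiling for loss after contrast, since patients failing on other criteria may never reach the CT, and some baseline scans may be standard of care.

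**2. Days lost after an aborted implant.** With discharge on day D, counted from the operation, collection ends at min(30, D), so 30 − D of the first 30 days are unobserved. The protocol gives no discharge day; the values of D are assumptions.

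| Assumed discharge day | Unobserved days | Share of 30 |
|---|---|---|
| 5 | 25 | 83% |
| 7 | 23 | 77% |
| 10 | 20 | 67% |
| 14 | 16 | 53% |

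**3. Neurological re-tests.** Table 4 sets windows at days 23–37, 53–67 and 83–97 after a neurological event. Take the most favorable case: an event on the day of operation and exit at the latest permitted day, 30. The second window opens 53 − 30 = 23 days after exit. The third runs from 83 − 30 = 53 to 97 − 30 = 67 days after exit. Later events push the windows further out, so neither can ever be met. The NIH Stroke Scale and Modified Rankin paragraph lists only 30 and 60 days, while Table 4 and the Neurological Dysfunction definition add 90. The 60-day check is missed under either version.

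**4. How much severity the contrast note spans.** Observation starts at baseline + 0.5 mg/dL. The acute creatinine criterion is exceeded above the lower of 3 × baseline and 5 mg/dL, if sustained beyond 48 hours. The chronic creatinine criterion starts at baseline + 2 mg/dL. Baselines are assumed.

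| Baseline (mg/dL) | Observation from | Acute above | Chronic from |
|---|---|---|---|
| 1.0 | 1.5 | 3.0 | 3.0 |
| 1.5 | 2.0 | 4.5 | 3.5 |
| 2.0 | 2.5 | 5.0 | 4.0 |

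Between the observation and dysfunction columns, the exemption is compatible with the definitions. At or beyond the dysfunction columns, the note and the definitions give opposite instructions and neither says which prevails.

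**5. Possible size.** No contrast-injury rate is given. For assumed rates p of 2%, 5%, 10% and 20%, and with every consented patient exposed, expected cases are 60p = 1.2, 3, 6 and 12. Among the 20 not implanted they are 20p = 0.4, 1, 2 and 4, with a chance of at least one of 1 − (1 − p)^20 = 33%, 64%, 88% and 99%. These are upper values for injury of any grade; the fraction severe enough to be in dispute is unknown. One event does matter at this sample size. With the plan's exact 95% interval and 60 exposed, 0/60 has an upper limit of 6.0%, while 1/60 (1.7%) has limits of 0.04% and 8.9%.

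**The case against.** **Screen failures.** Exit comes when screening is complete, and Table 3 footnote 3 places the renal check within one week of the CT, so the natural order is check first, exit second. This stands. A reader might infer that a patient is exited on the day the CT is read, or is released with an unresolved injury. The text says neither, and it requires follow-up to resolution. Nor can one say that exited patients have no form for the result: no scheduled follow-up visit exists for them, but the case report forms in Appendix K were not resubmitted. What remains is a missing cross-reference.

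**Contrast injury.** The note can be read as covering only the laboratory changes named just before it. The renal definitions carry no contrast exclusion, and the protocol provides for pre-implant and serious events. A dialysis case could therefore be reported, and milder injury is still recorded as an observation. So it is not established that severe cases are excluded. But the literal wording has no ceiling and stands inside the definition it would override, leaving each site to choose.

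**Aborted implants.** The 30-day split of deaths belongs to the primary safety measure, whose primary analysis includes only patients with the device placed. This is right for the primary analysis. It does not reach the secondary set, which is defined by having been followed up, or the neurological re-tests, which attach to any neurological event.

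**Deliberate choice.** Appendix V attributes both the nephropathy monitoring and the 30-day-or-discharge rule to regulator requests. That explains their presence; neither entry mentions the non-reporting rule or reconciles the sections.

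**Conclusion.** The point holds in three parts of unequal strength. For aborted implants, the text ends collection at discharge if that comes before day 30, and no permitted exit date accommodates the 60-day or later neurological checks. For contrast injury, the exemption lacks an upper limit and, read literally, conflicts with the renal definitions and the serious criteria. For screen failures, early loss is possible but not prescribed.

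A reader might infer that the primary safety result is biased. The documents do not support that: the composite counts device-related events adjudicated by the committee, and its primary analysis is confined to implanted patients. The exposure is in overall, serious and procedure-related tabulations and in the secondary analysis.

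The size of any under-count cannot be derived. The 20 non-implanted consents are a ceiling, discharge days and contrast rates are assumptions, and the number of aborted implants is not stated. This is an inexpensive improvement worth making, not a flaw that invalidates the study.

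**What to change.** 1. **Aborted implants** (Design; Screening and Patient Informed Consent): collect adverse events and vital status to day 30 or discharge, whichever is later. For any neurological event, complete the protocol's post-event checks, after reconciling the sections that differ on whether these end at 60 or 90 days.
2. **Contrast note** (CT Scan; Renal Dysfunction): limit observation-only recording to non-serious laboratory changes below the acute and chronic definitions. Report any case meeting either definition, or any serious criterion in Adverse Event Classification, as an adverse event for committee review, including cases before implantation.
3. **Screen failures** (Study Size and Duration; Screening and Patient Informed Consent; Pre-implant Preparation): state that exit is completed only after the post-CT renal check and any required renal follow-up, and name the form that holds the result.

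The cost is an amendment to wording, one day-30 contact per aborted implant, neurological re-tests for any such patient who has an event, and slightly later exits. The renal check is already mandatory, so no renal test is added. Reported event counts may rise slightly.
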